#### 6.2.4 Exploratory Efficacy Variables

- **Percent change from Baseline in facial papule lesion counts at each visit**

The percentage change from baseline in facial papule lesion counts at each visit (Weeks 2, 4, 8, 12, and 20) will be calculated.

- **Change from Baseline in facial papule lesion counts at each visit**

Change from baseline in facial papule lesion counts at each visit (Weeks 2, 4, 8, 12, and 20) will be calculated.

- **Percent change from Baseline in facial pustule lesion counts at each visit**

The percentage change from baseline in facial pustule lesion counts at each visit (Weeks 2, 4, 8, 12, and 20) will be calculated.

- **Change from Baseline in facial pustule lesion counts at each visit**

Change from baseline in facial pustule lesion counts at each visit (Weeks 2, 4, 8, 12, and 20) will be calculated.

- **Percent change from Baseline in facial nodule lesion counts at each visit**

The percentage change from baseline in facial nodule lesion counts at each visit (Weeks 2, 4, 8, 12, and 20) will be calculated.

- **Change from Baseline in facial nodule lesion counts at each visit**

Change from baseline in facial nodule lesion counts at each visit (Weeks 2, 4, 8, 12, and 20) will be calculated.

- **Change from Baseline in Truncal PGA for chest at each visit**

The Truncal PGA is a global assessment that will be used to assess the current state of AV on the chest, neck, and back at each visit. Each area will be evaluated and scored separately on a scale ranging from 0 (clear) to 4 (severe).

Change from baseline in Truncal PGA for chest at each visit (Weeks 2, 4, 8, 12, and 20) will be calculated.

The number and percentage of subjects who have Truncal PGA Grade 0, 1, 2, 3, 4 for chest at baseline and the shifts from baseline grades to each visit (Weeks 2, 4, 8, 12, and 20) will be calculated based on these values.

- **Change from Baseline in Truncal PGA for neck at each visit**

Change from baseline in Truncal PGA for neck at each visit (Weeks 2, 4, 8, 12, and 20) will be calculated.

The number and percentage of subjects who have Truncal PGA Grade 0, 1, 2, 3, 4 for neck at baseline and the shifts from baseline grades to each visit (Weeks 2, 4, 8, 12, and 20) will be calculated based on these values.

- **Change from Baseline in Truncal PGA for back at each visit**

Change from baseline in Truncal PGA for back at each visit (Weeks 2, 4, 8, 12, and 20) will be calculated.

The number and percentage of subjects who have Truncal PGA Grade 0, 1, 2, 3, 4 for back at baseline and the shifts from baseline grades to each visit (Weeks 2, 4, 8, 12, and 20) will be calculated based on these values.

- **Change from Baseline in overall Truncal PGA at each visit**

The overall Truncal PGA is determined from the average of Truncal PGA scores for 3 body areas in the form of a whole number, according to the definitions presented in **Table 6**.

Change from baseline in overall Truncal PGA at each visit (Weeks 2, 4, 8, 12, and 20) will be calculated.

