APPENDIX 9: PHYSICIAN'S GLOBAL ASSESSMENT

The PGA tool will be used to assess the following areas of the trunk: chest, back, and neck ([Section 8.1.7](#)). Individual PGA assessments will be made of each region.

Physician's Global Assessment (PGA) Trunk		
0	Clear	Clear skin with no inflammatory or non-inflammatory lesions
1	Almost Clear	A few scattered comedones and a few small papules.
2	Mild	Easily recognizable; less than half the surface is involved. Some comedones and some papules and pustules.
3	Moderate	More than half of the surface is involved. Many comedones, papules, and pustules. One nodule may be present.
4	Severe	Entire surface is involved. Covered with comedones, numerous papules and pustules. Few nodules may be present.

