**Table 6      Overall Truncal PGA**

Overall Truncal PGA	Average Score
0	0 (all component=0)
1	0 to <1.5
2	≥ 1.5 to <2.5
3	≥ 2.5 to <3.5
4	≥ 3.5

- **Proportion of subjects with at least 1-point decrease from Baseline in facial IGA at each visit**

For each treatment group, the number of subjects with at least 1-point decrease from baseline in facial IGA will be calculated at each visit (Weeks 2, 4, 8, 12, and 20). The proportion of such subjects will be calculated for each treatment group at each visit as:

$$\frac{\text{Number of subjects with (facial IGA at Week } x - \text{facial IGA at baseline)} \leq -1}{\text{Number of subjects in treatment group with baseline facial IGA score} \geq 1 \text{ and facial IGA at Week } x}$$

- **Proportion of subjects with at least 2-point decrease from Baseline in facial IGA at each visit**

For each treatment group, the number of subjects with at least 2-point decrease from baseline in facial IGA will be calculated at each visit (Weeks 2, 4, 8, 12, and 20). The proportion of such subjects will be calculated for each treatment group at each visit as:

$$\frac{\text{Number of subjects with (facial IGA at Week } x - \text{facial IGA at baseline)} \leq -2}{\text{Number of subjects in treatment group with baseline facial IGA score} \geq 2 \text{ and facial IGA at Week } x}$$

- **Proportion of subjects with at least 1-point decrease from Baseline in overall Truncal PGA at each visit for subjects with Baseline overall Truncal PGA score of at least 1**

For each treatment group, the number of subjects with at least 1-point decrease from baseline in overall Truncal PGA will be calculated at each visit (Weeks 2, 4, 8, 12, and 20). The proportion of such subjects will be calculated for each treatment group at each visit as:

$$\frac{\text{Number of subjects with (overall Truncal PGA at Week } x - \text{overall Truncal PGA at baseline)} \leq -1}{\text{Number of subjects in treatment group with baseline overall Truncal PGA} \geq 1 \text{ and overall Truncal PGA at Week } x}$$

- **Proportion of subjects with at least 2-point decrease from Baseline in overall Truncal PGA at each visit for subjects with Baseline overall Truncal PGA score of at least 2**

For each treatment group, the number of subjects with at least 2-point decrease from baseline in overall Truncal PGA will be calculated at each visit (Weeks 2, 4, 8, 12, and 20). The proportion of such subjects will be calculated for each treatment group at each visit as:

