$$\frac{\text{Number of subjects achieving a Truncal PGA for back of clear (0) or almost clear (1) with baseline Truncal PGA for back} \geq 2 \text{ at Week } x}{\text{Number of subjects in treatment group with baseline Truncal PGA for back} \geq 2 \text{ and Truncal PGA for back at Week } x}$$

- Proportion of subjects achieving an overall Truncal PGA of clear (0) or almost clear (1) with at least a 2-grade decrease from Baseline at each visit for subjects with Baseline overall Truncal PGA score of at least 2**

For each treatment group, the number of subjects achieving an overall Truncal PGA of clear (0) or almost clear (1) with at least a 2-grade decrease from baseline will be calculated at each visit (Weeks 2, 4, 8, 12, and 20). The proportion of such subjects will be calculated for each treatment group at each visit as:

$$\frac{\text{Number of subjects achieving an overall Truncal PGA of clear (0) or almost clear (1) with baseline overall Truncal PGA} \geq 2 \text{ at Week } x}{\text{Number of subjects in treatment group with baseline Truncal PGA for back} \geq 2 \text{ and Truncal PGA for back at Week } x}$$

- Proportion of subjects achieving improvement (“Much better” or “Very much better”) according to the PGI-C at each post-Baseline visit**

For each treatment group, the number of subjects achieving improvement (“Much better” or “Very much better”) according to the PGI-C will be calculated at each post-baseline visit specified in the Schedule of Activities in **Table 2**. The proportion of such subjects will be calculated for each treatment group at each post-baseline visit (Weeks 2, 4, 8, 12, and 20) as:

$$\frac{\text{Number of subjects with PGI-C of “Much better” or “Very much better” at Week } x}{\text{Number of subjects in treatment group with PGI-C at Week } x}$$

- **Proportion of subjects achieving improvement (“A little better”, “Much better” or “Very much better”) according to the PGI-C at each post-Baseline visit**

For each treatment group, the number of subjects achieving improvement (“A little better”, “Much better” or “Very much better”) according to the PGI-C will be calculated at each post-baseline visit specified in the Schedule of Activities in **Table 2**. The proportion of such subjects will be calculated for each treatment group at each post-baseline visit (Weeks 2, 4, 8, 12, and 20) as:

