### **7.5.3 Exploratory Efficacy Analyses**

The continuous data endpoints of change and percent change from baseline will be analyzed using the MMRM approach as described for the primary efficacy analysis in [Section 7.5.1](#). Summary statistics and the results of statistical testing at each visit will be provided for each continuous exploratory variable. In addition, the change from baseline in PGI-S and Truncal PGA (by body region as well as the overall and the worst score across three regions) will be summarized and analyzed by shift tables and ordinal logistic regressions as described in [Section 7.5.2.7](#). Baseline of the response variable will be added to the ordinal logistic regression model as a categorical variable. The overall Truncal PGA will be presented separately for all subjects, adolescents, and adults.

The frequency and percentage of subjects for subjects for categorical exploratory endpoints related to Truncal PGA (by body region as well as the overall and the worst score across three regions), facial IGA, PGI-C, PGI-S, SSQ, and SSRS will be summarized at each protocol-specified visit. For proportion of subjects in each response category for the SSQ and SSRS, the difference in distribution between each dose of imidolimab and placebo will be analyzed using the approach described for the proportion of subjects in each response category for the PGI-C in [Section 7.5.2.9](#). For other categorical exploratory endpoints, an unadjusted risk difference and 90% exact unconditional CIs will be estimated between each dose of imidolimab and placebo for all subjects and within each stratum for facial IGA at baseline (Grade 3 vs. 4); the common risk difference will also be tested using a generalized CMH test as described in [Section 7.5.2.8](#).

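### SAP Table 6 puts every regional score sum from 1 to 4 into overall Truncal PGA grade 1, so the exploratory overall endpoints cannot see most one-region change and can label a subject with a severe region almost clear

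*SAP*

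**What the plan says.** Chest, neck and back are each graded 0 to 4 at every visit. SAP 6.2.4 then defines a combined score: "The overall Truncal PGA is determined from the average of Truncal PGA scores for 3 body areas in the form of a whole number", following Table 6. The bands are:

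- overall 0 only when all three regions are 0
- overall 1 for any other average below 1.5
- overall 2 from 1.5 to below 2.5
- overall 3 from 2.5 to below 3.5
- overall 4 from 3.5

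Protocol Appendix 9 describes grade 1 (*almost clear*) as "A few scattered comedones and a few small papules" and grade 4 (*severe*) as "Entire surface is involved. Covered with comedones, numerous papules and pustules. Few nodules may be present".

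Four endpoints use the overall score: change from baseline, a decrease of at least 1 point, a decrease of at least 2 points, and "Proportion of subjects achieving an overall Truncal PGA of clear (0) or almost clear (1) with at least a 2-grade decrease from Baseline". The last two are headed as reported "at each visit for subjects with Baseline overall Truncal PGA score of at least 2". SAP section 8 lists all four as exploratory additions to the protocol. SAP 7.5.3 also plans shift tables, ordinal regression and categorical summaries of the Truncal PGA "by body region as well as the overall and the worst score across three regions".

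**The concern.** An average over three regions dilutes acne that sits in one of them, and the wide grade 1 band then removes most of what is left. Entry depends on facial acne only (Protocol 5.1), so acne in one truncal region, or none, is to be expected.

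Three things follow:

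- The overall change endpoint records zero for some large regional improvements.
- The two overall 2-grade endpoints exclude, by their headings, some subjects who have a moderate or severe region.
- The word attached to overall grade 1 does not carry its Appendix 9 meaning.

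At stake is how the overall truncal results would be read, not the trial's main conclusion.

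**Working it through.** **Enumeration from Table 6 (no assumptions).** Inputs: three regional scores, each 0 to 4, giving 5 × 5 × 5 = 125 patterns, and the Table 6 bands. An average below 1.5 means a sum below 4.5, so overall grade 1 is a sum of 1 to 4.

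1. Patterns by overall grade 0, 1, 2, 3, 4: 1, 34, 55, 31, 4 (total 125).
2. The 34 grade 1 patterns by worst region: 7 have a worst region of 1, 15 of 2, 9 of 3 and 3 of 4. So 15 + 9 + 3 = 27 contain a region of at least 2, 9 + 3 = 12 a region of at least 3, and 3 a region of 4. The 12 are the permutations of (3,0,0), (3,1,0) and (4,0,0).
3. One region affected at 1, 2, 3 or 4 gives averages of 1/3 = 0.33, 2/3 = 0.67, 3/3 = 1.00 and 4/3 = 1.33. All are overall 1. A fall from 4 to 1 in that region is an overall change of 1 − 1 = 0. Only complete clearance registers, and then as 1 point. Baseline overall can never be 2.
4. Reverse case: (4,4,0) has average 8/3 = 2.67, overall 3. (4,0,0) has average 1.33, overall 1. The drop is 2 grades to overall 1, so this is a 0/1 responder although one region stayed at 4.
5. A baseline condition of overall at least 2 admits 55 + 31 + 4 = 90 patterns. A condition of worst region at least 2 admits 117. The difference is the 27 in step 2.

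These are counts of possible patterns, not expected shares of subjects.

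**The printed 0/1 fraction.** In SAP 6.2.4 the heading and numerator of the overall 0/1 endpoint require a baseline overall score of at least 2, but the denominator requires a baseline back score of at least 2. Of the 125 patterns, 10 have back at least 2 with overall below 2, and 25 have overall at least 2 with back below 2. Read literally, a subject with acne only on the back at grade 2 or more enters the denominator but cannot be a responder.

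**Illustrative size.** The documents give no truncal data, so these inputs are assumed: back, chest and neck affected independently in 60%, 40% and 20% of subjects; affected grades 1 to 4 in 20%, 35%, 30% and 15%; each grade lost with probability 0.25 on placebo and 0.40 on active; 36 per arm; two-sided 0.10; baseline-adjusted ANCOVA at one visit.

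- Subjects with some region at least 2: 1 − (1 − 0.6 × 0.8)(1 − 0.4 × 0.8)(1 − 0.2 × 0.8) = 1 − 0.52 × 0.68 × 0.84 = 0.70. Subjects with baseline overall at least 2: about 22%.
- Power for change: about 34% for the Table 6 score, 73% for the unrounded mean, and 60 to 63% for the worst region. With prevalence from 50/30/10% to 70/50/30%, it is 27–42% for Table 6 and 61–81% for the unrounded mean.
- About 40% of subjects with a regional improvement of at least 2 grades show zero overall change.
- Among overall responders (0/1 with a 2-grade drop), about 78% still have a region of at least 2, about 19% a region of at least 3, and about 0.6% a region of 4.

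**The case against.** The strongest reply is that the plan already holds the remedy. Chest, neck and back keep their own change and 0/1 endpoints, and SAP 7.5.3 adds the worst score. A back that goes from 4 to 1 is a back responder and shows in the worst-region shift table. This stands. A reader might infer that the trial misses large regional improvements, but one summary of the data misses them, not the trial.

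A reader might also infer that most subjects with truncal acne drop out of the overall responder analyses. The 1-point endpoint needs only a baseline overall score of 1, which Table 6 gives to anyone with any truncal acne. The restriction applies to the two 2-grade endpoints.

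Nor does Table 6 contradict the sentence that introduces it. That sentence defers to the table, and reserving 0 for three clear regions looks deliberate: an average of 0.33 is not called clear.

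Finally, the worst-region score has a blind spot of its own, since (4,4,4) to (4,0,0) shows no change. This is fair, and it is why one score should not serve both purposes. What the reply does not remove is that the overall endpoints, as written, would still be reported with a grade 1 label that can cover a moderate or severe region. The worst-region score is also named in SAP 7.5.3 without being defined among the variables in 6.2.4.

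**Conclusion.** The concern holds as a minor point about the exploratory overall Truncal PGA endpoints added in the SAP. The structural part is exact and follows from Table 6 alone: one-region acne always scores overall 1, it cannot meet the headed baseline of 2, and 27 of the 34 patterns graded 1 contain a region of grade 2 or more. The denominator error in the overall 0/1 fraction is also plain from the text.

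The power and share figures depend on assumed prevalence, grade mix and effect, and on a single-visit ANCOVA where the SAP plans an MMRM. They show direction and rough size only. The documents claim no power for this endpoint, and its tests are exploratory.

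A reader might infer that severe regions are commonly hidden among overall responders. Under the same assumptions, a retained grade 4 region is rare (about 0.6%), and most retained disease is grade 2, which Appendix 9 calls mild. The primary, secondary and protocol-listed exploratory endpoints are not affected.

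**What to change.** 1. In SAP 6.2.4, use the unrounded mean of the three regional scores as the MMRM response for change from baseline in overall Truncal PGA. Keep the Table 6 grade only for the shift tables and ordinal regression, which need whole-number grades, and do not describe its grade 1 as *almost clear*.
2. Define the worst-region score in SAP 6.2.4 as the highest of the three regional grades. Base the overall 0/1 and 2-grade responder conclusions on it, with a worst-region baseline of at least 2 as the denominator. SAP 7.5.3 already plans analyses of this score.
3. Correct the denominator of the overall 0/1 endpoint in SAP 6.2.4, so that it no longer uses the back score and agrees with its heading and numerator.

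The cost is SAP wording and a short derivation, with no new data. The one small loss is that the change endpoint is no longer a whole-number grade.

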**Table 6      Overall Truncal PGA**

Overall Truncal PGA	Average Score
0	0 (all component=0)
1	0 to <1.5
2	≥ 1.5 to <2.5
3	≥ 2.5 to <3.5
4	≥ 3.5

- **Proportion of subjects with at least 1-point decrease from Baseline in facial IGA at each visit**

For each treatment group, the number of subjects with at least 1-point decrease from baseline in facial IGA will be calculated at each visit (Weeks 2, 4, 8, 12, and 20). The proportion of such subjects will be calculated for each treatment group at each visit as:

$$\frac{\text{Number of subjects with (facial IGA at Week } x - \text{facial IGA at baseline)} \leq -1}{\text{Number of subjects in treatment group with baseline facial IGA score} \geq 1 \text{ and facial IGA at Week } x}$$

- **Proportion of subjects with at least 2-point decrease from Baseline in facial IGA at each visit**

For each treatment group, the number of subjects with at least 2-point decrease from baseline in facial IGA will be calculated at each visit (Weeks 2, 4, 8, 12, and 20). The proportion of such subjects will be calculated for each treatment group at each visit as:

$$\frac{\text{Number of subjects with (facial IGA at Week } x - \text{facial IGA at baseline)} \leq -2}{\text{Number of subjects in treatment group with baseline facial IGA score} \geq 2 \text{ and facial IGA at Week } x}$$

- **Proportion of subjects with at least 1-point decrease from Baseline in overall Truncal PGA at each visit for subjects with Baseline overall Truncal PGA score of at least 1**

For each treatment group, the number of subjects with at least 1-point decrease from baseline in overall Truncal PGA will be calculated at each visit (Weeks 2, 4, 8, 12, and 20). The proportion of such subjects will be calculated for each treatment group at each visit as:

$$\frac{\text{Number of subjects with (overall Truncal PGA at Week } x - \text{overall Truncal PGA at baseline)} \leq -1}{\text{Number of subjects in treatment group with baseline overall Truncal PGA} \geq 1 \text{ and overall Truncal PGA at Week } x}$$

- **Proportion of subjects with at least 2-point decrease from Baseline in overall Truncal PGA at each visit for subjects with Baseline overall Truncal PGA score of at least 2**

For each treatment group, the number of subjects with at least 2-point decrease from baseline in overall Truncal PGA will be calculated at each visit (Weeks 2, 4, 8, 12, and 20). The proportion of such subjects will be calculated for each treatment group at each visit as:

$$\frac{\text{Number of subjects with (overall Truncal PGA at Week } x - \text{overall Truncal PGA at baseline)} \leq -2}{\text{Number of subjects in treatment group with baseline overall Truncal PGA} \geq 2 \text{ and overall Truncal PGA at Week } x}$$

- **Proportion of subjects achieving a Truncal PGA for chest of clear (0) or almost clear (1) with at least a 2-grade decrease from Baseline at each visit**

For each treatment group, the number of subjects achieving a Truncal PGA for chest of clear (0) or almost clear (1) with at least a 2-grade decrease from baseline will be calculated at each visit (Weeks 2, 4, 8, 12, and 20). The proportion of such subjects will be calculated for each treatment group at each visit as:

$$\frac{\text{Number of subjects achieving a Truncal PGA for chest of clear (0) or almost clear (1) with baseline Truncal PGA for chest} \geq 2 \text{ at Week } x}{\text{Number of subjects in treatment group with baseline Truncal PGA for chest} \geq 2 \text{ and Truncal PGA for chest at Week } x}$$

- Proportion of subjects achieving a Truncal PGA for neck of clear (0) or almost clear (1) with at least a 2-grade decrease from Baseline at each visit**

For each treatment group, the number of subjects achieving a Truncal PGA for neck of clear (0) or almost clear (1) with at least a 2-grade decrease from baseline will be calculated at each visit (Weeks 2, 4, 8, 12, and 20). The proportion of such subjects will be calculated for each treatment group at each visit as:

$$\frac{\text{Number of subjects achieving a Truncal PGA for neck of clear (0) or almost clear (1) with baseline Truncal PGA for neck} \geq 2 \text{ at Week } x}{\text{Number of subjects in treatment group with baseline Truncal PGA for neck} \geq 2 \text{ and Truncal PGA for neck at Week } x}$$

- Proportion of subjects achieving a Truncal PGA for back of clear (0) or almost clear (1) with at least a 2-grade decrease from Baseline at each visit**

For each treatment group, the number of subjects achieving a Truncal PGA for back of clear (0) or almost clear (1) with at least a 2-grade decrease from baseline will be calculated at each visit (Weeks 2, 4, 8, 12, and 20). The proportion of such subjects will be calculated for each treatment group at each visit as:

$$\frac{\text{Number of subjects achieving a Truncal PGA for back of clear (0) or almost clear (1) with baseline Truncal PGA for back} \geq 2 \text{ at Week } x}{\text{Number of subjects in treatment group with baseline Truncal PGA for back} \geq 2 \text{ and Truncal PGA for back at Week } x}$$

- Proportion of subjects achieving an overall Truncal PGA of clear (0) or almost clear (1) with at least a 2-grade decrease from Baseline at each visit for subjects with Baseline overall Truncal PGA score of at least 2**

For each treatment group, the number of subjects achieving an overall Truncal PGA of clear (0) or almost clear (1) with at least a 2-grade decrease from baseline will be calculated at each visit (Weeks 2, 4, 8, 12, and 20). The proportion of such subjects will be calculated for each treatment group at each visit as:

$$\frac{\text{Number of subjects achieving an overall Truncal PGA of clear (0) or almost clear (1) with baseline overall Truncal PGA} \geq 2 \text{ at Week } x}{\text{Number of subjects in treatment group with baseline Truncal PGA for back} \geq 2 \text{ and Truncal PGA for back at Week } x}$$

- Proportion of subjects achieving improvement (“Much better” or “Very much better”) according to the PGI-C at each post-Baseline visit**

For each treatment group, the number of subjects achieving improvement (“Much better” or “Very much better”) according to the PGI-C will be calculated at each post-baseline visit specified in the Schedule of Activities in **Table 2**. The proportion of such subjects will be calculated for each treatment group at each post-baseline visit (Weeks 2, 4, 8, 12, and 20) as:

$$\frac{\text{Number of subjects with PGI-C of “Much better” or “Very much better” at Week } x}{\text{Number of subjects in treatment group with PGI-C at Week } x}$$

- **Proportion of subjects achieving improvement (“A little better”, “Much better” or “Very much better”) according to the PGI-C at each post-Baseline visit**

For each treatment group, the number of subjects achieving improvement (“A little better”, “Much better” or “Very much better”) according to the PGI-C will be calculated at each post-baseline visit specified in the Schedule of Activities in **Table 2**. The proportion of such subjects will be calculated for each treatment group at each post-baseline visit (Weeks 2, 4, 8, 12, and 20) as:

$$\frac{\text{Number of subjects with PGI-C of “A little better”, “Much better” or “Very much better” at Week } x}{\text{Number of subjects in treatment group with PGI-C at Week } x}$$

- **Proportion of subjects achieving “Mild” or “Clear skin” according to the PGI-S at each visit**

For each treatment group, the number of subjects achieving “Mild” or “Clear skin” according to the PGI-S will be calculated at each visit specified in the Schedule of Activities in **Table 2**. The proportion of such subjects will be calculated for each treatment group at each visit (Weeks 0, 2, 4, 8, 12, and 20) as:

$$\frac{\text{Number of subjects with PGI-S of “Mild” or “Clear skin” at Week } x}{\text{Number of subjects in treatment group with PGI-S at Week } x}$$

- **Change from Baseline in PGI-S at each visit**

Change from baseline in PGI-S at each visit (Weeks 2, 4, 8, 12, and 20) will be calculated. The number and percentage of subjects who have PGI-S Grade 1, 2, 3, 4 at baseline and the shifts from baseline grades to each visit (Weeks 2, 4, 8, 12, and 20) will be calculated based on these values.

- **Proportion of subjects in each response category for the SSQ at each visit**

The SSQ asks subjects to rate their satisfaction with their acne condition on a 7-point scale from 0 (extremely dissatisfied) to 6 (extremely satisfied). It will be assessed at the visits specified in the Schedule of Activities in **Table 2**.

For each treatment group, the number of subjects in each response category for the SSQ will be calculated at each visit (Weeks 0, 2, 4, 8, 12 and 20). The proportion of such subjects will be calculated for each treatment group at each visit as:

$$\frac{\text{Number of subjects with SSQ of “extremely satisfied” at Week } x}{\text{Number of subjects in treatment group with SSQ at Week } x}$$

$$\frac{\text{Number of subjects with SSQ of “somewhat satisfied” at Week } x}{\text{Number of subjects in treatment group with SSQ at Week } x}$$

$$\frac{\text{Number of subjects with SSQ of “slightly satisfied” at Week } x}{\text{Number of subjects in treatment group with SSQ at Week } x}$$

$$\frac{\text{Number of subjects with SSQ of “neither satisfied nor dissatisfied” at Week } x}{\text{Number of subjects in treatment group with SSQ at Week } x}$$

$$\frac{\text{Number of subjects with SSQ of “slightly dissatisfied” at Week } x}{\text{Number of subjects in treatment group with SSQ at Week } x}$$

$$\frac{\text{Number of subjects with SSQ of "somewhat dissatisfied" at Week } x}{\text{Number of subjects in treatment group with SSQ at Week } x}$$

$$\frac{\text{Number of subjects with SSQ of "extremely dissatisfied" at Week } x}{\text{Number of subjects in treatment group with SSQ at Week } x}$$

- **Proportion of subjects achieving “slightly satisfied”, “somewhat satisfied,” or “extremely satisfied” according to the SSQ at each visit**

For each treatment group, the number of subjects achieving “slightly satisfied”, “somewhat satisfied”, or “extremely satisfied” according to the SSQ will be calculated at each visit (Weeks 0, 2, 4, 8, 12 and 20). The proportion of such subjects will be calculated for each treatment group at each visit as:

$$\frac{\text{Number of subjects with SSQ of "slightly satisfied", "somewhat satisfied", or "extremely satisfied" at Week } x}{\text{Number of subjects in treatment group with SSQ at Week } x}$$

- **Proportion of subjects in each response category for the SSRS at Week 12 and Week 20**

The SSRS asks subjects to rate their satisfaction with their study treatment on a 7-point scale from 0 (extremely dissatisfied) to 6 (extremely satisfied). It will be assessed at Weeks 12 and 20.

For each treatment group, the number of subjects in each response category for the SSRS will be calculated at Weeks 12 and 20. The proportion of such subjects will be calculated for each treatment group at Weeks 12 and 20 as:

$$\frac{\text{Number of subjects with SSRS of "extremely satisfied" at Week } x}{\text{Number of subjects in treatment group with SSRS at Week } x}$$

$$\frac{\text{Number of subjects with SSRS of "somewhat satisfied" at Week } x}{\text{Number of subjects in treatment group with SSRS at Week } x}$$

$$\frac{\text{Number of subjects with SSRS of "slightly satisfied" at Week } x}{\text{Number of subjects in treatment group with SSRS at Week } x}$$

$$\frac{\text{Number of subjects with SSRS of "neither satisfied nor dissatisfied" at Week } x}{\text{Number of subjects in treatment group with SSRS at Week } x}$$

$$\frac{\text{Number of subjects with SSRS of "slightly dissatisfied" at Week } x}{\text{Number of subjects in treatment group with SSRS at Week } x}$$

$$\frac{\text{Number of subjects with SSRS of "somewhat dissatisfied" at Week } x}{\text{Number of subjects in treatment group with SSRS at Week } x}$$

$$\frac{\text{Number of subjects with SSRS of "extremely dissatisfied" at Week } x}{\text{Number of subjects in treatment group with SSRS at Week } x}$$

- **Proportion of subjects achieving “slightly satisfied”, “somewhat satisfied”, or “extremely satisfied” according to the SSRS at Week 12 and Week 20**

For each treatment group, the number of subjects achieving “slightly satisfied”, “somewhat satisfied”, or “extremely satisfied” according to the SSRS will be calculated Week 12 and

Week 20. The proportion of such subjects will be calculated for each treatment group at each visit as:

$$\frac{\text{Number of subjects with SSRS of "slightly satisfied", "somewhat satisfied", or "extremely satisfied" at Week } x}{\text{Number of subjects in treatment group with SSRS at Week } x}$$

- **Proportion of subjects achieving a DLQI of 0 or 1 at each visit for subjects with Baseline DLQI of at least 2**

For each treatment group, the number of subjects achieving a DLQI of 0 or 1 with baseline DLQI of at least 2 will be calculated at each visit (Weeks 2, 4, 8, 12, and 20). The proportion of such subjects will be calculated for each treatment group at each visit as:

$$\frac{\text{Number of subjects achieving a DLQI of 0 or 1 with baseline DLQI } \geq 2 \text{ at Week } x}{\text{Number of subjects in treatment group with baseline DLQI } \geq 2 \text{ and DLQI at Week } x}$$

- **Proportion of subjects with less than 5 facial inflammatory lesion count (papules and pustules) at each visit**

For each treatment group, the number of subjects with less than 5 facial inflammatory lesion count (papules and pustules) will be calculated at each visit (Weeks 2, 4, 8, 12, and 20). The proportion of such subjects will be calculated for each treatment group at each visit as:

$$\frac{\text{Number of subjects with less than 5 facial inflammatory lesion count (papules and pustules) at Week } x}{\text{Number of subjects in treatment group with facial inflammatory lesion count (papules and pustules) at Week } x}$$

